4. GENERAL METHODOLOGY AND CONVENTIONS

4.1. Hypotheses and Decision Rules

Given the algorithm's intended use as a screening tool in the general population not guided by a healthcare professional, we would define the success criteria for the algorithm as achieving a sensitivity on par with that of a rapid antigen test for SARS-CoV-2 infection as observed in real world studies, which is between 60% and 80%¹. Hence, the success criteria for the algorithm will be an observed sensitivity of 70% or better.

The specificity of the algorithm will be assessed with a target minimum specificity of 60% as observed in other studies that use audio signals to detect SARS-CoV-2 infection². The goal is to optimize the sensitivity of the algorithm as the primary performance measure without compromising the minimum specificity, since this algorithm is meant to be used as a screening tool (high sensitivity) and not a diagnostic tool. The reference rapid antigen test benchmarks compared to RT-PCR test for SARS-CoV-2 are as follows¹: sensitivity $\geq 80\%$ in symptomatic individuals and sensitivity $\geq 60\%$ in asymptomatic individuals.

The probability that the observed sensitivity for symptomatic RT-PCR positive participants in AcRIS is greater than 70% with a total number of 100 cases is given in the following table for two assumed true values of expected sensitivity.

Table 1. Probability that observed sensitivity in symptomatic RT-PCR positive participants in AcRIS is greater than 70% with total of 100 cases.

[figure not shown]
True Sensitivity	Probability of Observed Sensitivity > 70% ¹
60%	0.02
75%	0.88
80%	0.99

Thus, with at least 100 symptomatic RT-PCR positive participants in AcRIS, we hypothesize that the study has high probability of success under these conditions.

Furthermore, Figure 1. illustrates the number of cases required to achieve target sensitivity values for a given screening tool – e.g., for a sensitivity of 70% with 10% margin of error for the 95% confidence interval (i.e., 60% to 80%), 81 cases are required (assuming a binomial distribution for the sensitivity values). Identifying 100 symptomatic positive cases should allow us to attain 70% target sensitivity with precision of 8.98%.

¹ Under the assumption of a binomial distribution.

Figure 1. Estimation of the number of cases required to achieve target sensitivity values assuming a 10% margin of error.

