4.2.5.1. Classical Machine Learning Model Training and Testing

The data will be randomly divided into two sets by subject: training (e.g., 80% of subjects) and test set (e.g., 20% of subjects). Repeated stratified k-fold cross validation (on the subject level) on the training data will be used to evaluate performance, as it provides confidence in the resulting performance values. Both k (number of folds) and n (number of repetitions) will be chosen based on the final sample size. The test set will be a hold-out test set until model training and validation is complete.

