4.2.5.2. Classical Machine Learning Model Selection

In order to evaluate model performance, predictions from each model will be summarized in a confusion matrix, as shown in Table 2. Performance metrics including *sensitivity*, *specificity* and *balanced accuracy* will be computed as shown in Table 3. Area under the receiver operating characteristic curve (AUC-ROC) showing *sensitivity* vs. $1 - \textit{specificity}$ will also be assessed. A proposed classical machine learning model will be chosen based on the repeated stratified k-fold cross validation performance. This model may be further tuned to maximize performance, will be trained on the entire training set to generate a final model, and will finally be tested on the hold-out test set to generate the final performance results.

Table 2. Confusion Matrix. True Positives (TP), True Negatives (TN), False Positives (FP), False Negatives (FN); in terms of total number among predictions.

		Actual	
		Positive	Negative
Predicted	Positive	TP	FP
	Negative	FN	TN

Table 3. Definition of Performance Measures. True Positives (TP), True Negatives (TN), False Positives (FP), False Negatives (FN).

Performance Measure	Formula
Sensitivity	$TP / (TP + FN)$
Specificity	$TN / (TN + FP)$
Balanced Accuracy	$(\text{Sensitivity} + \text{Specificity}) / 2$

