4.2.5.3. Classical Machine Learning Model Output

The final output of the classical machine learning approach will be the full set of model predictions for the best-performing model's repeated k-fold cross-validation, as well as the full set of predictions of this model on the hold-out test set. Both sets of predictions will be paired with their respective labels so that all performance metrics can be calculated.

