4.2.6.3. Deep Learning Model Training and Testing

The dataset will be divided into three separate datasets: training (e.g., 70% of data), validation (e.g., 10% of data) and test set (e.g., 20% of data). We will replicate the training and validation split three times at the subject level to ensure the results are not biased by single randomization. The training of the model requires the choice of an error function, so called a loss function, that can be used to estimate the loss of the model so that the parameters can be updated to reduce the loss on the next evaluation. Given that we have a binary classification problem (sick vs well), our loss function would be binary cross entropy, or weighted binary cross entropy. To optimize the parameters of the model, we will either use ADAM or Stochastic Gradient Descent (SGD) approach. The name ADAM is derived from adaptive moment estimation. ADAM uses momentum of the optimization object and adaptive learning rate to converge faster than SGD⁵³. We will use learning rates such as 0.001 or 0.0001 as the starting point.

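### The success probabilities and 8.98% precision in SAP Appendix A, 4.1 assume 100 tested cases, but the result called final comes from a hold-out subset of those cases (e.g. 20%)

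*SAP*

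**What the plan says.** SAP Appendix A, section 4.1 sets one pass mark: "Hence, the success criteria for the algorithm will be an observed sensitivity of 70% or better". Table 1 gives the probability that observed sensitivity exceeds 70% with 100 cases as 0.02, 0.88 and 0.99 for true sensitivities of 60%, 75% and 80%. The section then concludes that "with at least 100 symptomatic RT-PCR positive participants in AcRIS, we hypothesize that the study has high probability of success under these conditions". It adds that a 10-point margin at 70% sensitivity needs 81 cases, and that "Identifying 100 symptomatic positive cases should allow us to attain 70% target sensitivity with precision of 8.98" per cent. It does not say on which dataset the criterion is judged.

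The modelling sections divide the same cases. For classical machine learning (4.2.5.1): "The data will be randomly divided into two sets by subject: training (e.g., 80% of subjects) and test set (e.g., 20% of subjects"). The chosen model is trained on the whole training set and "will finally be tested on the hold-out test set to generate the final performance results" (4.2.5.2); section 4.2.6.4 says the same for deep learning. The deep learning split in 4.2.6.3 is "training (e.g., 70% of data), validation (e.g., 10% of data) and test set (e.g., 20% of data"). Section 5.1 applies the classical models to the Primary Analysis Set, and 5.2 does so for deep learning if the data allow. Section 3 defines that set as participants who start negative without acute symptoms and become positive and symptomatic.

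Two other sensitivity estimates are planned. Section 4.2.5.3 outputs the cross-validation predictions "as well as the full set of predictions of this model on the hold-out test set". Sections 4.6 and 5.5.2 test the models on Secondary Analysis Set B (positive and symptomatic at swab #1), whose size is not stated.

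**The concern.** A case used to train a model cannot also count as an independent test of that model. If the final sensitivity comes from a hold-out set, its precision and its chance of reaching 70% depend on the number of hold-out cases, not on all 100. Section 4.1 uses all 100.

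What is at stake is how the pass mark is read. On a small hold-out set, an algorithm at the bottom of the appendix's 60% to 80% antigen-test range can reach 70% by chance far more often than Table 1 suggests, and a good one can miss it more often. A reader would also attach the 8.98-point margin to a hold-out result that is much less precise.

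Two smaller gaps make the criterion harder to apply. The rule is 70% or better, while Table 1 gives the probability of strictly more than 70%. And Table 2 counts results "in terms of total number among predictions" without saying whether one prediction is a participant or a diary recording.

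**Working it through.** **Inputs.** From 4.1: pass mark 70%; true sensitivities 60%, 75% and 80%; 100 cases; 95% confidence. From 4.2.5.1 and 4.2.6.3: example test share 20%. Assumptions: exactly 100 cases and one call per participant.

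**1. Reproduce the plan's figures at n = 100.**

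- Normal approximation: P = 1 − Φ((0.70 − p)/√(p(1 − p)/n)).
  - p = 0.60: (0.70 − 0.60)/0.0490 = 2.04, so P = 0.021.
  - p = 0.75: −0.05/0.0433 = −1.155, so P = 0.876.
  - p = 0.80: −0.10/0.0400 = −2.50, so P = 0.994.
  - These round to the stated 0.02, 0.88 and 0.99.
- Half-width: 1.96 × √(0.7 × 0.3/100) = 0.0898, the stated 8.98%.
- Cases for a 10-point margin: 1.96² × 0.21/0.01 = 80.7, so 81.

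The arithmetic in 4.1 is therefore right for 100 independently tested cases.

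**2. Hold-out cases.** 20% × 100 = 20.

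**3. Same formulas with other denominators.** The exact columns are binomial tails, P(X ≥ 0.7n) and P(X > 0.7n). Each triplet is for true sensitivity 60/75/80%.

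| Tested cases | Normal, >70% (as Table 1) | Exact, ≥70% (the rule) | Exact, >70% | 95% half-width at 70% |
|---|---|---|---|---|
| 100 | 0.02 / 0.88 / 0.99 | 0.025 / 0.896 / 0.994 | 0.01 / 0.85 / 0.99 | 9.0 points |
| 80 (training cases) | 0.03 / 0.85 / 0.99 | 0.04 / 0.88 / 0.99 | 0.02 / 0.82 / 0.98 | 10.0 points |
| 30 (if 30% held out) | 0.13 / 0.74 / 0.91 | 0.18 / 0.80 / 0.94 | 0.09 / 0.67 / 0.87 | 16.4 points |
| 20 (20% held out) | 0.18 / 0.70 / 0.87 | 0.25 / 0.79 / 0.91 | 0.13 / 0.62 / 0.80 | 20.1 points |

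At n = 20 the half-width is 1.96 × √(0.21/20) = 0.201.

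**4. Exact interval at the pass mark.** For 14 of 20 the exact 95% interval is 45.7% to 88.1%, wider than the whole 60% to 80% benchmark range. For 70 of 100 it is 60.0% to 78.8%.

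**5. Cases needed to keep the stated precision.** At a 20% hold-out, the appendix's 81 tested cases need 81/0.20 = 405 in total, and 100 tested cases (8.98 points) need 100/0.20 = 500. At 30%, 81 tested cases need 81/0.30 = 270.

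**6. If recordings are counted instead of people.** With m recordings per person and within-person correlation ICC, the effective number for 20 people is 20m/(1 + (m − 1)ICC). Neither m nor ICC is in the documents; I assume m of 5 to 10 and ICC of 0.3 to 0.7.

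- m = 5, ICC 0.7: 100/3.8 = 26.3, half-width 17.5 points.
- m = 10, ICC 0.3: 200/3.7 = 54.1, half-width 12.2 points.

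Over that range the half-width stays 1.4 to 1.95 times the stated 8.98.

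**The case against.** The strongest reply is that this is an omission, not an error. Section 4.1 labels its figures as being for 100 cases, they reproduce, and it does not say the criterion is judged on the hold-out set. Cross-validation within the training data is also described as a way of evaluating performance. With about 80 cases it would give a half-width of 10.0 points and exact pass probabilities of 0.04, 0.88 and 0.99, close to Table 1. That comparison is fair. But cross-validation performance is also what selects the model, so it is optimistic, and 4.2.5.2 reserves the final result for the hold-out set. Set B lies outside the 100 cases and has no stated size.

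The n = 20 figures rest on example splits, and the case count may exceed 100. That stands, and the size depends on it. The direction does not: any hold-out set is smaller than the full set, and even 400 cases would put 80 in a 20% hold-out, a half-width of 10.0 points.

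Redaction is a real limit. One analysis set is blacked out, as are text in and after 4.6 and after 5.5.2. The main SAP's change table suggests that the redacted item was also extended to all positive cases. A link between the criterion and another dataset could sit there. It would not change what 4.1 claims or what 4.2.5.2 and 4.2.6.4 call final.

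On impact, main SAP 5.1 disclaims decision rules, and protocol 9.2 says only that the sample may suffice and will show what further data are needed. Under the rule as written, the loss at 75% and 80% is moderate (0.90 to 0.79 and 0.99 to 0.91); the large change is at 60%. The criterion is also a point estimate, so the wide interval does not itself cause failure. These points limit the consequences. They do not make the stated figures describe the final result.

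**Conclusion.** The concern holds on the visible text. The figures in 4.1 are correct for 100 independently tested cases but do not describe the hold-out result that the appendix calls final. With 100 cases, a 20% hold-out and one call per participant, the chance that a 60%-sensitive algorithm meets the stated rule rises from about 2% to 25%. The chance that a 75%-sensitive one fails it rises from about 10% to 21%. The half-width goes from 9.0 to 20.1 points. A larger hold-out or more cases would narrow the gap, but a 20% hold-out needs 500 cases before 8.98 points applies to it. Correction is advisable because 4.1 states an explicit pass criterion and draws a favourable conclusion from these numbers. Enrolment, the primary endpoints and safety are not affected.

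**What to change.** In SAP Appendix A, section 4.1:

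1. Name the dataset and unit for the 70% criterion, for example one call per participant in the hold-out test set.
2. Restate Table 1, the precision sentence and the conclusion about the probability of success for the expected number of hold-out cases, using 70% or better throughout. With 20 cases held out, the exact values are 0.25, 0.79 and 0.91, with a margin of about 20 points. Alternatively, keep the present figures and label them as applying to 100 independently tested cases.
3. Define a prediction in Table 2, and report sensitivity per participant, or with a participant-clustered confidence interval if recordings are counted.
4. Present the cross-validation and Set B results as supporting estimates.

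This costs wording and one recalculated table in the appendix. It needs no further participants or data. The restated figures will look less favourable.

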4.2. General Methods

4.2.1. Voice Data Preparation

Audio data collected during the performance of voice tasks (i.e., phonemes and reading) in the Electronic Diary will be processed as follows:

Automatic checks are performed in the Electronic Diary for duration and background noise, with the latter used to drive the speech signal to a desired signal-to-noise ratio for analysis with feedback provided to the user so corrective action may be taken during data collection. In addition, cleaning will be performed on the audio data before data analysis to remove leading and trailing background noise associated with the speech signal. The data pipeline performing feature extraction will at a minimum have the following functions:

1. *Auto-cleaning*: to remove leading or trailing noise artifacts, log cleaning success or failure, and log percent change to audio signal.
2. *Automatic transcription*: The transcript and timing of each spoken word from the reading task will be automatically derived using proprietary Amazon Web Services (AWS) speech-to-text technologies³. Transcription content may be compared to the expected reading passage using the Levenshtein ratio metric⁴ to measure differences between the transcribed speech and the canonical rainbow passage as a potential measure of incoming sample quality⁵.

4.2.2. Voice Feature Extraction

The following list of features will be extracted from each voice task using established routines⁶⁻⁸ for all participants in the FAS who have voice data and at least one RT-PCR test

result. Each audio task will be matched with an appropriate subset of these features. Short-duration phoneme tasks EE and MM will be paired with features from lists 1, 2, and 3 below which generally focus on power, pitch, and spectral structure. Sustained phonation task AHH will be paired only with feature 4.d, which will provide information related to lung capacity. The reading task will be paired with features 3.f and 4.a-c, which cover both spectral structure and measures related to shortness of breath and breathlessness.

1. Features capturing power and power variability in speech:
 - a. Shimmer
 - i. Local
 - ii. Local decibel (dB)
 - b. Third octave band energy
2. Features capturing pitch and pitch variability in speech:
 - a. Formants
 - i. Mean formant values for formants 1, 2, 3.
 - ii. Mean formant bandwidth values for formants 1, 2, 3.
 - b. Jitter
 - i. Local
 - ii. Local absolute
 - c. Coefficient of variation F0
 - d. Voiced frames
3. Features capturing spectral structure of speech:
 - a. Harmonicity
 - b. Entropy
 - c. Spectral flatness
 - d. Voiced low-to-high ratio
 - e. Cepstral peak prominence
 - f. Mel-frequency cepstral coefficients
 - i. Mean coefficients 1-13
 - ii. Standard deviation coefficients 1-13
 - iii. Delta coefficients 1-13
 - iv. Delta-delta coefficients 1-13
4. Features capturing information related to shortness of breath, breathlessness, and/or lung capacity.
 - a. Speaking rate
 - b. Number of pauses
 - c. Average pause length
 - d. Maximum phonation time

4.2.3. Feature Selection and Dimensionality Reduction Methods

The univariate analysis performed as part of the primary objective of the study and detailed in the main SAP will be employed on the features listed in [Section 4.2.2](#). This analysis will help inform which voice features and symptoms change with SARS-CoV-2 infection to guide the classical machine learning analysis described in [Section 4.2.6](#). To minimize the amount of noise or irrelevant information in model training, validation, and testing, both feature selection and dimensionality reduction methods will be used. This process will include

feature values paired with their respective sick and well labels (supervised learning) and may also include the symptom scores associated with each sample. This analysis will be performed on participants' data within the primary analysis set.

Clustering methods such as t-distributed Stochastic Neighbor Embedding (t-SNE)⁹, Uniform Manifold Approximation and Projection (UMAP)¹⁰, and/or 2-component Principal Component Analysis (PCA)¹¹ will be used to qualitatively investigate to what degree features and/or the combination of features and symptoms can separate the well and sick states. While the resulting clusters will not be used to directly remove certain features from consideration, they will help inform which features and/or symptoms group together, which will be useful in understanding how the final model makes predictions.

Feature and/or symptom correlations will provide an understanding of symmetrical linear relationships in the data. Features that are highly correlated with one another will be identified as features that could potentially be dropped, as they provide similar information. The Predictive Power Score (PPS)¹², which compares a feature's ability to predict another feature against the performance of a naïve classifier (e.g., choosing the most frequent class, choosing the median), will be used to investigate asymmetrical non-linear relationships among the features. Features with a PPS indicating low predictive utility (e.g., less than 0.1 using F1-score as an evaluation metric) will also be separated as features that can potentially be eliminated. Other metrics may also be used to assist in this analysis, such as the chi-square test, information gain, or random forest feature importance.

Once this process has been completed, automated feature elimination algorithms will be used iteratively to further remove any remaining redundant features. This will be accomplished with Recursive Feature Elimination with Cross Validation (RFECV)¹³, which recursively removes features until predictive performance degrades, and/or the Boruta algorithm¹⁴, which removes features that fail to perform better than a random classifier.

Finally, PCA may be used to perform dimensionality reduction by projecting the remaining features from a high-dimensional space m to a lower-dimensional space n . Depending on the size of the remaining feature set, if PCA can significantly reduce the number of features (e.g., $n < 75\%$ of the total number of features m) while maintaining a high degree of explained variance (e.g., $>95\%$), then it may be appropriately used to reduce the final feature set. Assuming PCA is deemed to be a viable option, both the resulting PCA features, that is, those n components that explain a high percent (e.g., $>95\%$) of the variance, *and* the features remaining after RFECV/Boruta will be used as separate inputs for performing the repeated stratified k -fold cross-validation outlined in [Section 4.2.6.1](#). This way, the cross-validation performances of the PCA feature set and the reduced feature set can be compared to ensure that this last dimensionality reduction step does not significantly impact performance.

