6.1.1. Main Analysis

6.1.1.1. Well to Sick

- Estimator: Primary Estimator E1(Section 2.1.1). This estimator is intended to provide a population level estimate of the well state as well as changes in symptoms and voice features from well to sick in symptomatic SARS-CoV-2, influenza virus, or RSV positive participants using Electronic diary.
- Analysis Sets: (a) Participants in Primary Analysis Set (Section 4) who become SARS-CoV-2, influenza virus or RSV positive (at Swab#2) and symptomatic during the study; (b) A subset of (a) who are symptom free at enrollment; (c) A subset of (a) who have symptoms due to chronic pre-existing conditions at enrollment. These analysis sets will be considered as deemed appropriate by data.
- Intercurrent events and missing data: (a) There are no particular intercurrent events considered. Participants who have events that lead to missing data will be included and missing data will not be imputed. (b) Inadequate compliance – data will be used as recorded.
- Statistical Method: Summary statistics and linear mixed effect analyses as described in Section 5.2.2.3. The total symptom score, each symptom and each voice feature will be modelled individually.
- Summaries:
 - a. Descriptive summaries and corresponding plots of the mean/SD will be provided. For linear mixed effect model analyses, estimates for all parameters fixed effect means, standard errors, 90% CIs, and p-values, as well as the variance estimates for their

random effects will be provided (as described in [Section 5.2.2.3](#)). Results from all models will be presented in a table.

- b. To assess the well-to-sick analysis baseline: For voice features that are determined as statistically significant based on linear model mixed effect analysis, the difference of the voice feature values between every pre-symptomatic day (starting from enrollment day) and the well-to-sick baseline (i.e. 7-day average before symptomatic onset as described in [Section 5.2.2.3](#)) will be computed. The mean/SD of the differences across participants in the analysis set will be plotted by day up to the symptomatic onset.

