4.2.5. Classical Machine Learning

Using the reduced feature set from Section 4.2.3., classical machine learning algorithms will be trained to perform the binary classification of well versus sick states. Ensemble learning algorithms are the preferred method because they: typically generalize well, are very robust to overfitting, can be trained efficiently, require little hyper-parameter tuning to achieve competitive results, perform predictions quickly and can be easily packaged for deployment²⁰. The classical machine learning approach also lends itself to making understandable predictions. SHapley Additive exPlanations (SHAP)²¹ will be used to investigate the most successful models to determine to what degree each feature influences model output. The main classical machine learning models of interest include: Random Forest²²; Bagging²³; Extreme Gradient Boosting (XGBoost)²⁴; Light Gradient Boosting Machine (LGBM)²⁵; Support Vector Machine (SVM) Ensemble²⁶.

Additional modeling may include a combination of spectrograms (described in Section 4.2.4.) and voice features described in Section 4.2.2. The spectrogram averaged across time may be combined with the voice features and used as the input to the classical machine learning model. In early fusion, a classifier is trained on the combined set of voice features and averaged spectrograms. In late fusion, separate models are trained on averaged spectrograms and voice features, and the final prediction is the average of the output from the two models²⁷⁻²⁹.

In addition, covariance approach which quantifies the linear relationship between features will also be explored to perform the binary classification of well versus sick states. This

approach has been shown to be invariant to the linear transformation of the features³⁰. This invariance property might diminish the intersubject variability of the acoustic features and can also reduce any learning effects of the acoustic features over time on the model performance. The input data for this approach will be the MFCCs matrix, as described in [Section 4.2.4](#).

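### Features are chosen with the sick/well labels before the cross-validation folds are formed, so the cross-validated performance of the feature-based models tends to be optimistic

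*SAP*

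**What the plan says.** adSAP 4.2.3 describes a supervised selection process that works on "feature values paired with their respective sick and well labels (supervised learning", with symptom scores as a possible addition. The data named are participants' "data within the primary analysis set", with no limit to training participants. "The univariate analysis performed as part of the primary objective of the study and detailed in the main SAP will be employed on the features"; main SAP 6.1.1.1 runs that analysis on all participants in its set who become "influenza virus or RSV positive (at Swab#2) and symptomatic during the study". Chi-square, information gain or forest importance may also be used. After that, "automated feature elimination algorithms will be used iteratively to further remove any remaining redundant features", by recursive feature elimination with cross-validation (RFECV) and/or Boruta.

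On what follows, 4.2.3 says that, if PCA is viable, the PCA components and the "features remaining after RFECV/Boruta will be used as separate inputs for performing the repeated stratified" k-fold cross-validation. With or without PCA, 4.2.5 says: "Using the reduced feature set from Section 4.2.3., classical machine learning algorithms will be trained".

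4.2.5.1 makes the split by participant (for example 80/20), runs the cross-validation on the training part to evaluate performance, and keeps the test set aside until training and validation are finished. It does not mention feature selection. 4.2.5.2 chooses the model on cross-validated performance and takes the final results from the hold-out set. 5.1 reports mean and SD for validation, and the test-set results separately.

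**The concern.** Cross-validation is honest only if nothing about the left-out participants went into building the model. In the order stated, their labels have already helped decide which features the model may use. Features that separate sick from well by chance in the full data are kept, and they then separate the left-out fold by the same chance.

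The figures affected decide which classical model goes forward and appear in the report. The feature-based versions of the analyses in 4.4 and 4.5 inherit the problem, because they are trained as in 4.2.5. The plan also sets targets that such figures will be read against: 70% sensitivity and a 60% minimum specificity (4.1).

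**Working it through.** **1. Order of the steps.** Let D be the training participants and F one fold. The estimate for F should come from features chosen on D without F. Under 4.2.3 and 4.2.5 the features come from D including F, or from the whole Primary Analysis Set. Either way F's labels were used, so making the 80/20 split first does not remove the problem. RFECV's internal cross-validation does not remove it either, because the reported k-fold run starts from the already reduced set. The cross-references do not settle the order: 4.2.3 sends the reader to 4.2.6.1 for the cross-validation, and that section is Pre-Training.

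**2. The plan's own figures.** The plan gives no figure for this bias. Its precision statement in 4.1 reproduces: 1.96 × √(0.7 × 0.3 / 100) = 0.0898, the stated 8.98%. A 20% hold-out of 100 cases has about 20 cases, and 1.96 × √(0.21 / 20) = 0.20, counting one prediction per case. The cross-validated figure will look the more precise of the two and is likely to carry weight.

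**3. Number of candidate features (4.2.2).** EE and MM have 70 each: shimmer 2, third-octave energy counted as 1, formants 6, jitter 2, F0 variation 1, voiced frames 1, five single spectral measures, and 4 × 13 = 52 cepstral coefficients. AHH has 1. Reading has 52 + 3 = 55. The total is 70 + 70 + 1 + 55 = 196.

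**4. Illustrative simulation.** Assumptions that are not in the documents: 100 cases, 80 for training; 5 participant-level folds; features correlated 0.6 in blocks of 14; five diary days per state; within-person correlation 0.45, with half of the remaining variance shared within a state. Weak signal means 10 features shifted by 0.3 SD. The split is made first. The classifiers are on the plan's list ("The main classical machine learning models of interest include: Random Forest" and, further on, an SVM ensemble). The excess is cross-validated balanced accuracy with selection before the folds, minus the same with selection nested in the folds.

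| Selector and classifier | Setting | Excess | Runs |
|---|---|---|---|
| RFECV, random forest | five days, no signal | 0.06 | 40 |
| RFECV, random forest | five days, weak signal | 0.06 | 28 |
| RFECV, SVM ensemble | five days, no signal | 0.10 | 35 |
| RFECV, SVM ensemble | five days, weak signal | 0.09 | 23 |
| Boruta, random forest | one sample per state, correlated features | 0.00 | 21 |
| Boruta, random forest | five days | 0.04 | 9 |

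Standard errors are 0.006–0.008 (forest), 0.008–0.016 (SVM) and about 0.01 (Boruta). RFECV with one sample per state gave 0.08–0.09 (forest) and 0.10–0.17 (SVM). Those values are set aside because adSAP section 3 defines multi-day windows.

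**5. Check against the truth rather than the nested figure.** With no signal and five days, nested sensitivity was 0.49 (forest) and 0.48 (SVM), slightly below 0.50. Early selection gave 0.55 and 0.57, so the excess over chance is 0.05 and 0.07. With weak signal, cross-validated sensitivity/specificity against new participants was:
- forest: 0.66/0.65 against 0.62/0.59, balanced accuracy 0.655 − 0.605 = 0.05;
- SVM: 0.77/0.75 against 0.68/0.66, balanced accuracy 0.76 − 0.67 = 0.09.

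**6. A second, simpler simulation, for direction only.** It used t-test ranking and a shrunken linear discriminant, neither of which is the plan's method. With no signal and selection on training participants before the folds, cross-validated sensitivity was 0.59–0.62, against 0.49–0.51 nested. Hold-out sensitivity was 0.50–0.51 when selection used training participants only and 0.57–0.62 when it used the whole set. The hold-out result therefore depends on which participants enter selection; the cross-validated result is inflated in both cases.

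**The case against.** The strongest reply is that 4.2.5.2 takes the final results from the hold-out set, so what is certainly affected is a validation and model-choice figure. That stands, and it limits the point. A reader might infer that the plan's final performance figure is biased, or that the 70%/60% targets would be falsely met. The documents do not establish either. 4.2.3 names the whole Primary Analysis Set, but the protection of the test set in 4.2.5.1 can be read to cover selection as part of training. Section 4.1 does not say which estimate decides.

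Other replies:
- Boruta may be used instead of RFECV, and its bias here was small. This stands, although those runs needed a fallback rule when no feature was accepted, and that rule is not in the SAP.
- The univariate analysis only informs the work, and no section drops a feature on its result. This stands; it matters only if it is used to keep or drop features.
- Secondary Analysis Sets A and B lie outside the selection data. This stands in part. A supplies only well states and B only sick states, and neither corrects the model choice or the figures in 5.1. Redacted text in 4.6 may hold further tests.
- The study is exploratory. That lowers the stakes, but 4.1 still sets a success criterion.

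A reader might also extend the point to all models. Spectrogram, audio and MFCC-covariance inputs do not pass through 4.2.3 and are unaffected unless fused with selected features.

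**Conclusion.** The concern holds for the cross-validated sensitivity and specificity of the feature-based models. In the stated order these tend to be optimistic, whether or not the 80/20 split comes first. The size cannot be derived from the documents. Under the assumptions above it is about 0.06 to 0.10 in balanced accuracy with RFECV and multi-day data, and 0.00 to 0.04 with Boruta alone across the settings run. It also differs between classifiers, so it could sway the choice of model as well as the reported level.

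For the hold-out result the concern is conditional: it is biased only if selection uses the whole Primary Analysis Set, as 4.2.3 literally reads. The direction follows from the order of steps; the size rests on assumed correlations, signal and number of days.

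**What to change.** In adSAP 4.2.3 and 4.2.5.1:
- Make the participant-level split before any step that uses the labels.
- Run RFECV, Boruta and any label-based filter (chi-square, information gain, forest importance) in training participants only, repeated within each cross-validation fold.
- Recompute on training participants any univariate result used to keep or drop features.
- Correct the cross-references in 4.2.3: 4.2.6 should be 4.2.5, and 4.2.6.1 should be 4.2.5.1.

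This changes SAP wording and the order of the code, with no new data. Selection is repeated in every fold, so computing time rises, and the reported cross-validated figures will probably be lower.
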